10.3 Reporting of SAEs And Unexpected Adverse Reactions

The qualified investigator will be responsible for classification of an AE as an SAE within 24 hours of notification. Causality should be signed off by the qualified investigator prior to reporting to ethics and regulatory bodies. Notification of any serious adverse events must be made in writing to the study sponsor. The IRB will be notified of all diet related SAEs and unexpected adverse reactions. All blinded SAE's or unblinded-participant-on-active product SAE's will be reported to the Therapeutics Products Directorate (TPD) in an expedited manner.

KGK Science must notify the TPD of all blinded or unblinded-participant-on-active product serious adverse events and reactions as follows:

If it is neither fatal or life threatening, within 15 calendar days after the day on which the sponsor becomes aware of the information; and

If it is fatal or life threatening, must be reported as soon as possible, but not later than seven (7) days after the day on which the sponsor becomes aware of the information.

11 STATISTICAL EVALUATION

11.1 Determination of Sample Size

Because this is a pilot study to explore the efficacy and safety of Nic's Ketogenic Diet, sample size will not be calculated. A total of 14 participants will be enrolled.

11.2 Analysis Plan

The **Safety Population** will consist of all participants who start the diet, and on whom any safety information is available.

The **Intent-to-Treat (ITT) Population** will consist of all participants who start the diet and on whom efficacy information is available.

The **Per Protocol (PP) Population** will consist of all participants who comply with the diet, do not have any major protocol violations and complete all study visits and procedures connected with measurement of the primary variable.

11.3 Statistical Analysis Plan

All test of significance will be performed at 2-sided, alpha level = 0.05 unless otherwise specified.

All the primary and secondary endpoints will be analysed as continuous variables.

For each primary and secondary endpoint, descriptive statistics including number of subjects, arithmetic mean, standard deviation, median, minimum and maximum values will be presented for each study day and for the changes from baseline (Day 0) to each subsequent study day.

Changes in continuous endpoints from baseline will be calculated as:

$$\text{Change to } V_i = \text{Value at } V_i - \text{Value at } V_{\text{baseline}}$$

The continuous endpoints will be analysed with Mixed Model for Repeated Measures (MMRM). The model will include baseline value and visit as independent variables. P-values for the changes from baseline will be obtained from the model. No adjustment on p-values for multiple primary endpoints will be made.

Missing data for the primary and secondary endpoints will be imputed with last-observation-carried-forward (LOCF) method or multiple imputation as a sensitivity analysis for ITT Population. No imputation will be performed for PP and Safety Population.

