1.3 Schedule of Assessments

Procedures	Visit 1 Screening	Visit 2 Day 0 (Baseline)	Visit 3–7 Day 28–112 Week 4–16	Visit 8 Day 140 Week 20
Informed consent	X			
Review inclusion/exclusion criteria	X	X		
Review medical history	X			
Review concomitant therapies	X	X	X	X
Vitals: Height*, weight, heart rate, blood pressure *Height will only be measured at visit 1	X	X	X	X
Urine pregnancy test	X	X		X
Physical examination		X		
Blood collection for analysis of: CBC, electrolytes (Na ⁺ , K ⁺ , Cl ⁻ , P), HbA1c, fasting glucose, eGFR, creatinine, AST, ALT, total bilirubin, and TSH *TSH will only be measured at visit 1	X			X
DEXA scan** **DEXA will be measured at Visits, 2, 5 and 8 only		X	X	X
ECG** **ECG will be measured at Visits, 2, 5 and 8 only		X	X	X
Blood Markers: Fasting glucose, HbA1c, C-reactive protein, lipid panel, Free Tri-iodothyronine (T3), ESR		X		X
Lipid Panel	X		X	
Nutritional Counselling [#] and dispense Nic’s Keto Diet e-book #As required, remote Nutritional Counselling will be completed on 3-day food records weekly throughout study period		X		
Daily glucose monitors, and keto monitors Dispensed		X	X	
Daily glucose monitors, and keto monitors Returned			X	X
Food Records Dispensed	X	X	X	
Food Records Returned		X	X	X
Subject Diary Dispensed		X	X	
Subject Diary Returned			X	X
Compliance Calculated			X	X
Adverse Events	X	X	X	X

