9.6 Visit 8 – End-of-Study (Day 140 ± 3 days)

Participants will return to the clinic after a 12-hour fast to complete end of study assessments with completed food records and subject treatment diary.

Visit 8 assessments include:

1. Collection and review of subject treatment diary
2. Collection and review of food records
3. Compliance calculation
4. Collection and review of glucose and ketone monitors
5. Collection of fasted ketone and glucose and review of glucose and ketone monitors
6. Review of concomitant therapies and adverse events
7. Weight measurements and BMI calculation (Section 9.5.1)
8. Seated resting blood pressure and heart rate measurements (Section 9.5.2)
9. Total body DEXA scan and ECG
10. Urine pregnancy test for female potential participants that are of child-bearing potential
11. Collection of fasted blood samples for the analysis of CBC, electrolytes (Na⁺, K⁺, Cl⁻, P), HbA1c, eGFR, creatinine, AST, ALT, total bilirubin, fasting glucose, C-reactive protein, lipid panel, free tri-iodothyronine (T3), and ESR

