9.9 Laboratory Analyses

Blood samples will be drawn from the participants at screening (Visit 1), baseline (Visit 2, Day 0), Visit 3, Visit 4, Visit 5, Visit 6, Visit 7, and at the End of Study visit (Visit 8, day 140) as indicated in the schedule of assessments.

Protection of subject confidentiality will extend to all data generated from the assaying of these samples. These samples will be alphanumerically coded and the persons performing the analysis will not be aware of the subject's identity.

At screening (Visit 1), 13 mL of ≥ 12 hours fasted whole blood will be collected in:

1. Two 4mL EDTA vacutainer tubes to generate plasma for:
 - a. CBC analysis (one tube)
 - b. Hb1Ac analysis (one tube)

2. One 5mL SST vacutainer tube to generate serum for:
 - a. Electrolytes (Na⁺, K⁺, Cl⁻, P), lipid profile, fasting glucose, eGFR, creatinine, AST, ALT, TSH, and total bilirubin

At baseline (Visit 2), 13 mL of ≥ 12 hour fasted whole blood will be collected in:

1. Two 4mL EDTA vacutainer tubes to generate plasma for:
 - a. Hb1-Ac (one tube)
 - b. ESR (One Tube)
2. One 5mL SST vacutainer tube to generate serum for:
 - a. Fasting glucose, C-reactive protein, lipid panel, Free T3 (one tube)

At Visit 3, 5 mL of ≥ 12 hour fasted whole blood will be collected in:

1. One 5mL SST vacutainer tube to generate serum for:
 - a. Lipid Panel (one tube)

At Visit 4, 5 mL of ≥ 12 hour fasted whole blood will be collected in:

1. One 5mL SST vacutainer tube to generate serum for:
 - a. Lipid Panel (one tube)

At Visit 5, 5 mL of ≥ 12 hour fasted whole blood will be collected in:

1. One 5mL SST vacutainer tube to generate serum for:
 - a. Lipid Panel (one tube)

At Visit 6, 5 mL of ≥ 12 hour fasted whole blood will be collected in:

1. One 5mL SST vacutainer tube to generate serum for:
 - a. Lipid Panel (one tube)

At Visit 7, 5 mL of ≥ 12 hour fasted whole blood will be collected in:

1. One 5mL SST vacutainer tube to generate serum for:
 - a. Lipid Panel (one tube)

At the end of the study (Visit 8), 17 mL ≥ 12 hour fasted whole blood will be collected in:

1. Three 4mL EDTA vacutainer tubes to generate plasma for:
 - a. CBC analysis (one tube)
 - b. Hb1Ac analysis (one tube)

c. ESR (One Tube)

2. One 5mL SST vacutainer tube to generate serum for:
 - a. Electrolytes (Na⁺, K⁺, Cl⁻, P), fasting glucose, eGFR, creatinine, AST, ALT, CRP, Lipid Panel, Free T3, and total bilirubin (one tube)

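### Single-arm p-values for change come from a model adjusted for baseline; read at mean baseline, its standard error is too small for testing zero population mean change

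*Combined protocol and SAP*

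**What the plan says.** Section 11.3 sets the level: "All test of significance will be performed at 2-sided, alpha level = 0.05 unless otherwise specified". Continuous endpoints go into an MMRM, and "The model will include baseline value and visit as independent variables". The test is given in one sentence: "P-values for the changes from baseline will be obtained from the model". The section does not name the model response (value or change), say whether Day 0 is a level of visit, or state the contrast and the baseline value at which it is read. Change is defined as visit value minus baseline, but that definition follows the descriptive statistics and is not tied to the model.

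The same section promises that "descriptive statistics including number of subjects, arithmetic mean, standard deviation, median, minimum and maximum values will be presented for each study day", and likewise for changes from baseline. Missing ITT data are to be handled by LOCF or multiple imputation, and "No imputation will be performed for PP and Safety Population".

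Section 11.1 enrols 14 participants in a pilot with no sample-size calculation. There is no comparator. Section 5 makes the changes in ESR and CRP the primary outcomes. Both are drawn at baseline and Visit 8 only: the relevant row of the schedule in section 1.3 is "Blood Markers: Fasting glucose, HbA1c, C-reactive protein, lipid panel, Free Tri-iodothyronine (T3), ESR", marked at those two visits. Section 9.6 repeats the draw at Day 140 ("total bilirubin, fasting glucose, C-reactive protein, lipid panel, free tri-iodothyronine (T3), and ESR"), and the tube lists in section 9.9 show only a lipid panel at Visits 3 to 7.

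**The concern.** Adjusting change for baseline is standard in a two-arm trial, because the term for the sample mean baseline cancels in the difference between arms. With one arm nothing cancels. The estimate at the mean baseline is the raw mean change, but its model standard error covers only the scatter about the regression line. It ignores the fact that the mean baseline of 14 people is itself a random quantity. If the p-value is read as a test that mean change in the population is zero, it is too small.

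This bears on both primary outcomes. With one post-baseline value the MMRM collapses to a simple regression of change on baseline, so the problem applies without modification. HbA1c, laboratory fasting glucose and free T3 are in the same position.

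**Working it through.** The plan states no power, SD or correlation, so there is no figure of its own to reproduce beyond the nominal 0.05.

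**Inputs from the documents.** n = 14 (section 11.1); two-sided 0.05 and baseline as covariate (section 11.3); one post-baseline value for ESR and CRP (sections 1.3, 9.6, 9.9).

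**Assumptions.** ρ = correlation of the Day 0 and Day 140 values; k = SD(Day 140)/SD(Day 0); normal data; true mean change zero; complete data. Change is the response and is read at the observed mean baseline.

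**Step 1, variances.** Set SD(Day 0) = 1. The slope of change on baseline is b = ρk − 1. The residual variance is k²(1 − ρ²), so the model variance of the mean change is k²(1 − ρ²)/n. The true variance is (1 + k² − 2ρk)/n. The difference is (ρk − 1)²/n, which is b²·Var(baseline)/n.

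**Step 2, ratio of model to true variance.** R = k²(1 − ρ²)/(1 + k² − 2ρk). At k = 1 this is (1 + ρ)/2. R never exceeds 1 and equals 1 only when ρk = 1, that is b = 0.

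**Step 3, attained level.** The model's t statistic times √R follows a t distribution with n − 2 = 12 df. The attained level is therefore P(|t₁₂| > 2.179·√R).

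Example, k = 1 and ρ = 0.5: R = 0.75; 2.179 × 0.866 = 1.887; level 8.4%.

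| ρ (k = 1) | R | Attained level | True SE / model SE = 1/√R |
|---|---|---|---|
| 0.2 | 0.60 | 11.7% | 1.291 |
| 0.5 | 0.75 | 8.4% | 1.155 |
| 0.8 | 0.90 | 6.1% | 1.054 |
| 0.9 | 0.95 | 5.5% | 1.026 |

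Simulation with 200,000 trials per setting agrees (11.8%, 8.2%, 6.0%, 5.5%). The paired t-test on normal, complete data gave 4.9% to 5.1%.

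**Step 4, unequal SDs.** At ρ = 0.5 the level is 17.8%, 12.6%, 8.4%, 6.2%, 5.4% and 5.0% for k = 0.67, 0.8, 1, 1.25, 1.5 and 2. Over ρ = 0.2, 0.5, 0.8, 0.9 crossed with these six ratios, it runs from 5.0% to 22.1% (the latter at ρ = 0.9, k = 0.67).

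**Step 5, missing data.** With 10 complete participants and no imputation, the equal-SD levels are 11.2%, 8.1%, 6.0% and 5.5%. LOCF for ESR or CRP carries the Day 0 value forward and gives zero change. If 4 of 14 are carried forward (an assumption), the levels fall to about 8.8%, 7.0%, 5.5% and 5.0%.

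**Step 6, non-normal data.** Lognormal values with log-SD 0.5 and the same distribution at both visits give 13.9%, 10.8%, 8.7% and 8.0% at log-scale correlation 0.2, 0.5, 0.8 and 0.9; the paired t-test gives 4.4% to 4.5%. Heavy-tailed changes (t with 3 df) with b = 0 give 4.2% for both tests. The direction is therefore guaranteed only under normality.

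**Step 7, endpoints with several visits.** With six post-baseline visits (weight, BP, lipids), equal SDs and an unstructured covariance, the level is 10.8%, 8.6%, 6.6% and 5.6% at ρ = 0.3, 0.5, 0.7 and 0.9. With two post-baseline visits (DEXA) and compound symmetry, the Day 140 level is 10.9%, 8.4%, 6.1% and 5.5% at ρ = 0.3, 0.5, 0.8 and 0.9.

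**The case against.** The best defence is that the plan states no hypothesis or estimand. Conditional on the observed baselines the test is nominal, so a reader who infers that the model is invalid in every sense goes too far. That stands. But the conditional test concerns the change expected at this sample's own mean baseline. Section 5 words the outcome simply as change in ESR and CRP and does not announce that narrower target.

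A reader might also take 18% or 22% as the size of the problem. The documents do not support that. Those figures need the Day 140 SD to fall to about two thirds of baseline, and no section suggests it will. Nor is 18% a ceiling, since the grid reaches 22.1%. For LDL-C the spread could move the other way: entry is limited to 2.5–4.1 mmol/L and the introduction expects LDL to rise. If k is 1.25, the level is only 5.0% to 6.2% at correlation 0.5 to 0.9.

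A third inference would be that every reading of section 11.3 fails. That is not so. With Day 0 in the response and no baseline covariate the level is 4.9% to 5.1%. With the covariate kept, unconstrained compound symmetry gave 5.0%, but an unstructured fit with a common slope is degenerate. A random intercept bounded at zero is mildly anti-conservative, by an amount that depends on the df rule. These readings are less natural, since change at Day 0 is identically zero. They do show that the text leaves the matter open.

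Finally, this is an exploratory pilot with no multiplicity adjustment and no decision rule tied to p, and the promised n, mean and SD of change let anyone compute the paired t-test. That limits the harm, but the reported p-value would still be the model's.

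**Conclusion.** The point holds for the natural reading: change as response, read at the mean baseline. For the hypothesis of zero population mean change, the planned standard error leaves out b²·Var(baseline)/n, and under normality the nominal 5% test is anti-conservative unless b = 0. Both primary outcomes are affected directly. With equal SDs, complete data and n = 14, the attained level is about 5.5% at correlation 0.9 and 8.4% at 0.5, rising to 11.7% at 0.2. Correlations and SD ratios are assumptions throughout. The effect is small when the SDs are equal and the correlation is high, and LOCF reduces it. It is worth correcting before analysis, but it does not undermine the study.

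**What to change.** State in section 11.3 the model response, how Day 0 enters and the contrast tested.

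- **ESR, CRP, HbA1c, laboratory fasting glucose, free T3:** test the Day 140 minus Day 0 change with a paired t-test, without the baseline covariate.
- **Weight, BP, lipids, DEXA:** use a repeated-measures model with Day 0 in the response, no baseline covariate, visit-minus-Day-0 contrasts, a small-sample df method such as Kenward-Roger, and a pre-specified simpler covariance fallback. The fallback is needed because an unstructured matrix over seven visits has 7 × 8/2 = 28 parameters for 14 participants (6 for the three DEXA visits). This model keeps partial follow-up that visit-by-visit paired tests would drop.

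The cost is one paragraph of wording and no new data. For ESR and CRP the standard error grows by about 15%, 5% and 2.6% at correlation 0.5, 0.8 and 0.9 with equal SDs. If the Day 140 SD is 0.67 times baseline it grows by 52% to 69%, so the loss of apparent precision is largest where the inflation is largest. That increase is the uncertainty the planned model leaves out. With strongly skewed data (lognormal, log-SD 1) the paired t-test is somewhat conservative, at 3.0% to 3.4%.

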5 STUDY OBJECTIVES

The objective of this study is to investigate the efficacy of Nic's Ketogenic Diet on cardiovascular health and inflammation in healthy adults with mildly elevated LDL-C.

Primary outcomes:

The change in inflammation, as assessed by the change in erythrocyte sedimentation rate (ESR) and C-reactive protein (CRP) following Nic's Keto Diet for 140 days. The main outcome of the study is to investigate whether in periods of higher LDL there will be positive impacts on cardiovascular health and inflammation.

Secondary outcomes:

Changes to the following parameters from baseline to day 140 at monthly intervals following Nic's Keto Diet:

1. Weight
2. Blood pressure (BP)
3. Lipid panel

Changes to the following parameters from baseline to days 70 and 140 following Nic's Keto Diet:

1. Body composition (total body fat (%), android fat (%), gynoid fat (%), android/gynoid fat ratio, and muscle mass (%)) as assessed by DEXA Scan

[figure not shown]
Changes to the following parameters from baseline to day 140 following Nic's Keto Diet:

1. HbA1c
2. Fasting glucose
3. Free Tri-iodothyronine (T3)

Safety outcomes:

1. Incidence of pre-emergent and post-emergent adverse events
2. Electrocardiogram (ECG) after 70 and 140 days of following Nic's Keto Diet
3. Vital signs: heart rate (HR)
4. Anthropometrics: BMI calculation
5. Clinical chemistry: alanine aminotransferase (ALT), aspartate aminotransferase (AST), total bilirubin, creatinine, electrolytes (Na⁺, K⁺, Cl⁻, P), HbA1c, fasting glucose, and estimated glomerular filtration rate (eGFR))
6. Hematology: white blood cell (WBC) count with differential (neutrophils, lymphocytes, monocytes, eosinophils, basophils), red blood cell (RBC) count, hemoglobin, hematocrit, platelet count, RBC indices (mean corpuscular volume (MCV), mean corpuscular hemoglobin (MCH), mean corpuscular hemoglobin concentration (MCHC), red cell distribution width (RDW), and mean platelet volume (MPV))

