9.2 Visit 2 – Baseline (Day 0)

Eligible participants will return to the clinic for baseline assessments after a 12-hour fast.

Baseline (Day 0) assessments include:

1. Collection and review of food records
2. Assessment of inclusion and exclusion criteria

3. Physical exam
4. Review of concomitant therapies and adverse events
5. Urine pregnancy test for female potential participants that are of child-bearing potential
6. Weight measurements and BMI calculation (Section 9.5.1)
7. Seated resting blood pressure and heart rate measurements (Section 9.5.2)
8. Total body DEXA scan
9. Collection of fasted blood for analysis of glucose, HbA1c, C-reactive protein, lipid panel, Free tri-iodothyronine (T3), and ESR.
10. Deliver Nutrition Counselling about Nic's Keto Diet (Section 9.7.7)
11. Dispense Nic's Keto Diet e-book
12. Dispense glucose and ketone monitors and instruct participants on their use. First fasted ketone and glucose measure to be taken with monitors during baseline clinic visit.
13. Dispense or assign dates of 3-day food records
14. Dispense participant treatment diary and instruct participants on use

The next visit will be scheduled for day 28.

Reminders for participants prior to their next in-clinic visit:

1. Return to the clinic in a 12-hour fasted state
2. Complete 3- day food records weekly. Weekly records will be reviewed by nutrition team and counselling provided as required.
3. Participants will receive a 2-week follow up email from Nutrition Team (Section 9.7.7).
4. Abide by instructions for medications as per Section 7.3.1 and OTC medications, supplements, and food and drinks as per Section 7.3.2.
5. Complete subject treatment diary
6. Maintain similar physical activity and study diet
7. Monitor glucose and ketones daily

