9.3 Visits 3 – 4 (Days 28, 56 ± 3 days)

Participants will return to the clinic after a 12-hour fast to complete assessments for Visits 3–4 with completed food records and subject treatment diary.

Assessments for Visits 3–4 include:

1. Collection and review of subject treatment diary
2. Collection and review of food records
3. Compliance calculation
4. Review of concomitant therapies and adverse events
5. Collection of fasted ketone and glucose and review of glucose and ketone monitors
6. Seated resting blood pressure and heart rate measurements
7. Weight measurement and BMI calculation (Section 9.5.1)
8. Collection of blood sample for lipid panel analysis (Section 9.5.2)
9. Dispense or assign dates of 3-day food records
10. Re-dispense subject treatment diary

The next visit will be scheduled for day 70

Reminders for participants prior to their next in-clinic visit:

1. Return to the clinic in a 12-hour fasted state
2. Complete 3-day food records weekly. Weekly records will be reviewed by nutrition team and counselling provided as required.
3. Abide by instructions for medications as per Section 7.3.1 and OTC medications, supplements, and food and drinks as per Section 7.3.2.
4. Complete subject treatment diary
5. Maintain similar physical activity and study diet
6. Monitor glucose and ketones daily

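### For ESR, CRP and the other endpoints with one scheduled post-baseline value, LOCF either assumes no change without saying so or imputes nothing when a participant has no sample after Day 0

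*Combined protocol and SAP*

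**What the plan says.** Section 11.3 analyses each continuous endpoint with an MMRM containing baseline and visit. Missing primary and secondary values are to be "imputed with last-observation-carried-forward (LOCF) method or multiple imputation as a sensitivity analysis for ITT Population"; nothing is imputed for the Per Protocol and Safety populations. The section does not choose between the two methods, does not say whether a Day 0 value may be carried forward, and makes no distinction between endpoints measured at many visits and endpoints measured once after baseline.

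Section 5 names the changes in ESR and CRP over 140 days as primary. In the Schedule of Assessments (section 1.3) the row "Blood Markers: Fasting glucose, HbA1c, C-reactive protein, lipid panel, Free Tri-iodothyronine (T3), ESR" is marked at Visits 2 and 8 only. Section 9.2 takes these markers at Day 0 ("Collection of fasted blood for analysis of glucose, HbA1c, C-reactive protein, lipid panel, Free tri-iodothyronine (T3), and ESR"). The Day 140 draw in section 9.6 includes "fasting glucose, C-reactive protein, lipid panel, free tri-iodothyronine (T3), and ESR". Between them, sections 9.3 to 9.5 list only "Collection of blood sample for lipid panel analysis".

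Three provisions can add a later value. Section 7.4 asks for the end-of-treatment evaluations at withdrawal where possible. Section 10.2.2 keeps some participants attending visits after they stop the diet. Section 9.9 allows additional or repeat samples.

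**The concern.** LOCF needs an earlier post-baseline value to carry. For these five endpoints the schedule provides none before Day 140. A participant who misses Day 140 and has no exit, off-treatment or repeat sample offers only the Day 0 value (or, for HbA1c and glucose, a screening value before it). Carrying Day 0 forward records a change of exactly zero. Not carrying it leaves the value missing.

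In the first case an assumption of no change enters without being named, and the inserted zeros are treated as if measured, so the interval is too narrow. In the second case the sensitivity analysis is the main analysis again.

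This matters somewhat because the MMRM for ESR and CRP, having a single post-baseline visit, reduces to a baseline-adjusted analysis of the observed Day 140 values. No interim readings of the same marker help it, so the sensitivity analysis is where the missing-data assumption would be examined. Withdrawals are not replaced (section 7.4), and each participant is 1/14 = 7% of the sample.

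**Working it through.** **Inputs.** n = 14, single group (section 11.1); two-sided alpha 0.05 (section 11.3). Section 11.1 states that "sample size will not be calculated", and no effect, SD or dropout rate is given, so there is no planned figure to reproduce. I assume k = 1 to 4 missing of 14 and true mean changes of 0.5 and 1 SD.

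**Step 1: is there really one post-baseline value?** The volumes in section 9.9 sum to 13 + 13 + 5×5 + 17 = 68 mL, which matches the stated total of about 68 mL. A 4 mL ESR tube at each of Visits 3 to 7 would give 68 + 20 = 88 mL. CRP does not appear in the Visit 3 to 7 tube lists. No interim ESR or CRP is planned.

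**Step 2: what LOCF does for a participant with nothing after Day 0.**
- Day 0 may be carried: change = Day 0 − Day 0 = 0.
- Only post-baseline values may be carried: nothing is imputed, and the difference from the observed-data analysis is exactly 0.
- The ITT definition in section 11.2 is applied endpoint by endpoint: the participant is outside ITT for that marker, and again nothing is imputed.

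**Step 3: size if Day 0 is carried and missing participants resemble completers.** With m = 14 − k completers whose mean change is d (SD 1), the LOCF mean is d × m/14, a shrinkage of k/14: 7.1%, 14.3%, 21.4% and 28.6% for k = 1 to 4. This holds for any distribution.

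Worked case, d = 0.5 and k = 4:
- Mean = 0.5 × 10/14 = 0.357.
- Sum of squares = 9×1 + 10×0.25 − 14×0.357² = 9.714, so SD = √(9.714/13) = 0.864 and SE = 0.864/√14 = 0.231.
- LOCF half-width = 2.160 × 0.231 = 0.499 SD. Completers alone: 2.262/√10 = 0.715 SD. Fourteen observed values with SD 1 would give 2.160/√14 = 0.577 SD. The interval with four inserted zeros is narrower than complete data would yield.
- p = 0.146 with LOCF against 0.148 for completers.

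**Step 4: coverage of the LOCF 95% interval** (simulation, normal changes, missing completely at random, 400,000 trials per cell):

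| True change | k=1 | k=2 | k=3 | k=4 |
|---|---|---|---|---|
| 0.5 SD | 95.1% | 94.4% | 92.9% | 90.3% |
| 1 SD | 95.0% | 92.7% | 88.4% | 81.9% |

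Completers' intervals cover 94.9% to 95.1%. LOCF type I error is 5.0%, 4.9%, 4.8% and 4.7% for k = 1 to 4. Power at 0.5 SD with 3 missing is 31.7% with LOCF and 32.4% for completers.

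Coverage depends on shape. With skewness 2 and 4 missing it is 79% (0.5 SD) and 71% (1 SD) if the long tail lies in the direction of the change, and 96% and 90% if it lies the other way. The completers' own interval then covers only about 92%.

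**Step 5: does multiple imputation add anything?** A second simulation fitted the baseline-adjusted model in 40,000 trials per cell, with 20 imputations and assumed predictor coefficients −0.4, 0.3 and 0.3. It took k = 1 to 4, true changes of 0.5 and 1 SD, and missing participants with 100%, 50% or 0% of the completers' change: 24 cells. Unshifted imputation gave the main model's average estimate to within 0.001 SD in all 24, so by itself it varies nothing. When missing participants truly had no mean change, shifting the imputed changes to no mean change left a bias of at most 0.004 SD, with coverage 97.3% to 99.7%.

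**The case against.** The strongest reply is that carrying Day 0 forward is informative. Set beside the MMRM, it contrasts no change with missing at random, which is a legitimate sensitivity comparison. If missing participants truly had no mean change, LOCF is nearly unbiased (at most 0.003 SD) with coverage 95.3% to 97.1%. The main model and unshifted imputation are then biased by 0.037 to 0.145 SD (true change 0.5 SD) or 0.072 to 0.286 SD (1 SD). This stands. What remains is that the plan does not declare the assumption and that the interval understates uncertainty if missing participants resemble completers.

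A reader might infer that LOCF can only ever give a zero or nothing for these markers. The documents do not support that: an exit evaluation (section 7.4), an off-treatment Day 140 visit (section 10.2.2) or a repeat sample (section 9.9) could supply a real later value.

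A reader might also infer that LOCF is the only check, or that the main result rests on it. Neither follows. Section 11.3 names multiple imputation on equal terms and adds a Per Protocol analysis without imputation. Its sentence most naturally makes both imputation methods sensitivity analyses.

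Finally, the conditions stack up: LOCF is chosen, Day 0 is carried, no later sample exists, and the participant counts as ITT for that marker. The number of subjects is to be reported and discontinuations listed (sections 11.3 and 11.3.1), so a reader could largely undo the shrinkage of the mean. That argues for a minor rating and does not remove the point.

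**Conclusion.** The point holds for ESR, CRP, free T3, HbA1c and laboratory fasting glucose, and only for ITT participants with no value after Day 0. For them LOCF is either an unstated no-change assumption or no imputation.

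If Day 0 is carried and missing participants resemble completers, the mean change shrinks by 7% to 29% for 1 to 4 missing. Coverage is hardly affected with 1 missing and falls to about 90% (0.5 SD) or 82% (1 SD) with 4 missing. The coverage figures rest on assumed effects, assumed missing counts and normal changes.

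It would be wrong to conclude that the primary test is invalid: the main MMRM is unaffected, and type I error and power barely move. Severity is minor, in a 14-person pilot. It is still worth correcting, because a better method is already permitted and needs no new data.

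**What to change.** In section 11.3, for ESR, CRP, free T3, HbA1c and laboratory fasting glucose:

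1. Remove LOCF.
2. Keep the observed-data, baseline-adjusted model as the main ITT analysis. State that it uses participants with a post-baseline value, and report how many lack one.
3. Make multiple imputation the sensitivity analysis and name its model in advance. The Day 0 value with the last available weight and LDL-C changes is one workable choice; keep it small, since 10 to 13 people would inform it if 1 to 4 are missing.
4. Pre-specify a shift of the imputed changes toward zero, for example by half and then by all of the main-model mean change, the full shift being no mean change. State at which baseline value that mean change is evaluated. The simulation above used the population mean, which an analyst will not know; at the sample mean the biases were similar but the observed-data interval covered 92.4% to 93.7%.
5. Report the results side by side as a range of estimates and intervals, not as further tests.
6. Say how exit and off-treatment samples enter the analysis.

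The cost is a few sentences and a little programming. In the simulation, intervals for 1 to 4 missing were wider than the observed-data interval by about 6% to 29% unshifted, 7% to 31% at the half shift and 8% to 36% at the full shift, and they were conservative. With 3 missing and a true change of 0.5 SD, the full-shift interval excluded zero in 10.6% of trials against 33.8% for the main model, which is why it should not be read as a test.
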